Cardiorespiratory Fitness and the Apolipoprotein E (ApoE) Genotype and Its Interaction with Cognitive Functions and Cognitive Decline in Late-Middle-Aged Older Adults: A Prospective Study

Principal Investigator: [name]

NTC: NCT05652140
Date: 2022/12/12

Aim:

This study utilized a longitudinal design to examine naturalistic changes in cardiorespiratory fitness (CRF) over an 18-month period as well as the interaction of CRF with apolipoprotein E gene (ApoE4) on a task that modulates inhibitory control demand in a community-dwelling sample of middle age and older adults. Specifically, we conducted a registered analysis using a data-driven 2×2 factorial design to compare changes in behavioral and neuroelectric indices of inhibitory control between four middle aged and older adult groups: (1) ApoE $\epsilon 4$ carriers displaying increases in CRF over 18-months, (2) ApoE $\epsilon 4$ non-carriers displaying increases in CRF over 18-months, (3) ApoE $\epsilon 4$ carriers displaying decreases in CRF over 18-months, and (4) ApoE $\epsilon 4$ non-carriers displaying decreases in CRF over 18-months. It was hypothesized that adults displaying increases in CRF would show more positive changes in inhibitory control outcomes than older adults displaying decreases in CRF. Further, such differences in the outcome measures of inhibitory control between the groups displaying increases and decreases in CRF were hypothesized to be greater in ApoE $\epsilon 4$ carriers.

METHODS

Design and Sample

This prospective study examining CRF and neurocognitive function at baseline and 18-month follow-up in 50–70-year-old adults was registered at ClinicalTrials.gov (NCT05652140). The actual conduct of this study was from 7/1/2018 to 5/1/2021.

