Potential participants were recruited via advertisements and personal contact from New Taipei City and Taipei City, Taiwan. Initially, this study included data from 159 participants who were (1) 50–70-years-old, (2) right-hand dominant, did not report (3) psychiatric and neurological disorders, (4) cardiovascular disease, (5) risk of performing physical activities, as measured by Physical Activity Readiness Questionnaire (PAR-Q)¹, had (6) normal color vision, (7) corrected-to-normal or normal vision based on the 20/20 standard, and a (8) Mini-Mental Status Examination (MMSE) score $\geq 25^2$. Due to the substantial overlapping of the study period with the COVID-19 pandemic, a larger-than-expected number of participants withdrew following completion of the baseline stage, resulting in a final sample of 83 with complete data for the registered longitudinal analysis.

Cardiorespiratory fitness assessment

CEF was measured via a braked cycle ergometer (Ergoselect 100/200 Ergoline GmbH, Germany) using the YMCA submaximal test including three or more 3-min

consecutive cycling stages according to ACSM's exercise testing guidelines³. Participants were fitted with a Polar heart rate (HR) monitor (Polar RS800CS; Polar Electro, Kempele, Finland) to continuously monitor their HR and provided ratings of perceived exertion⁴ every two minutes throughout the exercise testing. Participants were instructed to cycle at a power of 25 W (pedaling rate: 50 revolutions per minute [rpm]) for the initial three minutes, and HR recorded at the end of the last minute of the initial 3-min stage was used to determine the workload of the following stages of cycling. The test was terminated if two consecutive steady-state target HRs (i.e., between 110 beat per minute [bpm] and 85% of the age-predicted maximal HR [220 – age]) were reached. Estimated $\dot{V}O_{2\text{max}}$ ($\text{mL}\cdot\text{kg}^{-1}\cdot\text{min}^{-1}$) was then calculated using an established equation³. Participants whose $\dot{V}O_{2\text{max}}$ improved and deteriorated from the baseline to the 18-month follow-up were classified as 'Gaining-Fitness' and 'Losing-Fitness' groups, respectively.

Stroop test

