window width = 200ms, window step = 10ms) or signals that exceeded $\pm 100\mu\text{V}$ were rejected. After visually inspecting the accepted epochs, the mean amplitude P3 components were derived using 400 – 600ms post-stimulus windows, respectively. The Regions of interest was created to investigate parietally (P3/Pz/P4) centered P3 components.

Genetic data collection and processing

Licensed medical technologists collected 2-ml Ethylenediaminetetraacetic acid venous blood samples from the participants. DNA extraction and genotyping were conducted at the Union Clinical Laboratory, Taipei. ApoE genotyping was identified via sequencing rs429358 (ApoE C112R) and rs7412 (ApoE R158C) for three ApoE alleles(s) ($\epsilon 2$, $\epsilon 3$ and $\epsilon 4$) using the real-time polymerase chain reaction. The ApoE4 Carrier group was defined as participants who possessed $\epsilon 3/\epsilon 4$ or $\epsilon 4/\epsilon 4$, while the ApoE4 Non-Carrier group included those who possessed $\epsilon 2/\epsilon 2$, $\epsilon 2/\epsilon 3$, $\epsilon 2/\epsilon 4$, or ApoE $\epsilon 3/\epsilon 3$.

Procedure

Participants were invited to visit the laboratory on two separate days that were 18-month apart. Prior to each laboratory visit, participants were instructed to avoid vigorous exercise for at least 24 hours and consuming alcohol or caffeine at least 6 hours.

Baseline Visit: Participants completed the informed consent, demographic questionnaires, Digit Span Forward and Backward test¹¹, MMSE, PAR-Q, and the computerized Stroop test with simultaneous neuroelectric assessments in a sound-attenuated and dimly lit room, followed by the cardiorespiratory fitness assessment. 18-Month Follow-up Visit: Participants returned to the lab to complete the same protocol at 18 ± 3.32 months after the baseline visit along with a separate visit to the medical clinic to identify ApoE genotypes.

Statistical Analysis Plan:

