Analyses were performed using SPSS v.26 (SPSS Inv., Chicago, IL) with a family-wise alpha threshold set at $p = .05$. A two-way ANOVA, with ApoE4 Carriage (Carrier vs. Non-carrier) and changes in CRF (Δ Fitness Group) (Gaining-Fitness vs. Losing-Fitness) as between-subjects factors and Gender as a covariate, was conducted to analyze the demographic and physical outcomes. A similar three-way ANOVA including Congruency (Congruent vs. Incongruent) as an additional within-subjects factor, was used to analyze the baseline cognitive outcomes (response time, response accuracy, and P3 amplitude). A similar three-way ANOVA was conducted to analyze the difference scores for the cognitive outcomes (Δ response time, Δ response accuracy, and Δ P3 amplitude). Greenhouse Geisser and Bonferroni corrections were used when the sphericity assumption was violated and multiple comparisons were required. Effect sizes were reported using partial eta squared (η_p^2) and Cohen's d ¹². The baseline data were presented as means and standard deviations. The change in fitness and neurocognitive outcomes were presented as mean and standard error.

Reference:

1. American College of Sports Medicine. ACSM's Guidelines for Exercise Testing and Prescription. 11th ed. Philadelphia: Lippincott Williams and Wilkins 2022.
3. American College of Sports Medicine. ACSM's guidelines of exercise testing and prescription. 9 ed: Lippincott Williams & Wilkins 2014:1-456.
4. Borg GA. Psychophysical bases of perceived exertion. *Med Sci Sports Exerc* 1982;14:377–81.
6. Rey-Mermet A. Finding an interaction between Stroop congruency and flanker congruency requires a large congruency effect: A within-trial combination of conflict tasks. *Atten Percept Psychophys* 2020;82(5):2271-301. doi: 10.3758/s13414-019-01914-1 [published Online First: 2020/01/25]

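### The difference-score models name Gender as the only covariate, so age and follow-up interval may confound the Fitness-group main effect

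*Combined protocol and SAP*

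**What the plan says.** The Aim section describes a study to "examine naturalistic changes in cardiorespiratory fitness (CRF) over an 18-month period". Its first hypothesis concerns the fitness groups: "It was hypothesized that adults displaying increases in CRF would show more positive changes in inhibitory control outcomes" than those whose fitness fell. Under Cardiorespiratory fitness assessment, participants whose estimated VO2max rose or fell between visits "were classified as 'Gaining-Fitness' and 'Losing-Fitness' groups, respectively".

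The Statistical Analysis Plan names one covariate. In the two-way ANOVA, carriage and fitness group enter "as between-subjects factors and Gender as a covariate"; that model "was conducted to analyze the demographic and physical outcomes". For change, the plan says only "A similar three-way ANOVA was conducted to analyze the difference scores for the cognitive outcomes". That Gender is carried over has to be inferred from the word similar. If it is not carried over, there is less adjustment still.

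Design and Sample admits ages 50 to 70. Procedure places the second visit "at 18 ± 3.32 months after the baseline visit", without saying whether the figure after ± is a standard deviation or a window. Neither age nor interval appears as a covariate anywhere, and no rule says what happens to the change models if the demographic comparison shows an imbalance.

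**The concern.** When people sort themselves into gaining and losing fitness, the groups can differ in other ways that bear on cognition. A difference score cancels an effect of age on the level of performance if that effect is the same at both visits. It does not cancel an effect of age on the rate of change. Elapsed time can act on both sides: a longer interval leaves more time for fitness to change and for cognition to change.

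If the losing-fitness group is older, or was followed for longer, part of its cognitive change would be credited to fitness. The contrast at risk is the Fitness-group main effect, which is the first hypothesis. A Gender-only model gives no means of separating the two explanations.

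**Working it through.** The plan states no effect size, standard deviation or power, so there is no figure of its own to reproduce. The check asks how strong the confounding must be before it matters.

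**Inputs from the documents:** 83 participants analysed; ages 50 to 70; interval 18 ± 3.32 months; factors ApoE4 and Fitness with Gender as covariate; alpha 0.05.

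**Assumed, because the documents give none:** no true fitness effect; age spread evenly over 50 to 70; fitness groups of about equal size (split at the median change); 20% or 50% carriers, independent of age; and two correlations, *a* (age with fitness change) and *b* (age with outcome change).

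**Age, by hand.** A median split on an approximately normal variable separates the halves by 2√(2/π) = 1.596 SD. The age gap between groups is therefore 1.596·*a* SD, and the bias in the group difference is 1.596·*a*·*b* SD of the change score. With 41.5 per group the standard error is √(2/41.5) = 0.220 SD. One SD of age is 20/√12 = 5.77 years.

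- 0.2/0.2: gap 0.32 SD (1.8 years), bias 0.06 SD, bias/SE 0.29, false-positive rate about 6.0%.
- 0.3/0.3: gap 0.48 SD (2.8 years), bias 0.14 SD, bias/SE 0.65, about 10.0%.
- 0.4/0.4: gap 0.64 SD (3.7 years), bias 0.26 SD, bias/SE 1.16, about 21.4%.

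**Age, by simulation** of the between-subjects model (ApoE4, Fitness, their interaction, Gender; 10,000 runs per setting). Rejections for the Fitness main effect at nominal 5%, age omitted:

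| *a*/*b* | 20% carriers | 50% carriers |
|---|---|---|
| 0.1/0.1 | 4.8% | 4.8% |
| 0.2/0.2 | 5.6% | 5.5% |
| 0.3/0.1 | 5.2% | 5.6% |
| 0.3/0.3 | 8.1% | 9.7% |
| 0.4/0.4 | 15.3% | 21.8% |

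With age in the model the rate is 4.7 to 5.3%. Independent repeats gave the same pattern (8.0 to 10.2% at 0.3/0.3; 15.4 to 20.9% at 0.4/0.4).

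**Interaction.** With age omitted, the ApoE4 × Fitness test rejects in 4.6 to 5.6% of runs at every setting. If age relates to outcome change in carriers only (0.4/0.4), it rejects in 7.0 to 8.6% without age, 6.8 to 9.0% with age alone, and 4.0 to 4.9% with age and age × ApoE4.

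**Interval.** If 3.32 is an SD, ±2 SD spans 18 − 6.64 = 11.4 to 18 + 6.64 = 24.6 months. If it is a window, the span is 14.7 to 21.3 months. Suppose outcomes change on average by *d* SD per 18 months and the groups differ by *g* months; the bias is *d*·*g*/18. For *d* = 0.2 and *g* = 1 this is 0.01 SD; for *d* = 0.8 and *g* = 3 it is 0.13 SD.

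**Cost of adjusting.** Residual degrees of freedom fall from 83 − 5 = 78 to 83 − 7 = 76. With two irrelevant covariates, simulated confidence intervals widen by a factor of 1.013 to 1.014.

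**The case against.** The strongest reply is that no confounding is documented. Every correlation above is assumed, and with balanced groups the bias is nil. At weak correlations the error rate stays close to nominal; clear inflation needs both at about 0.3 or more. All of this stands, and it limits how strongly the point can be put.

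A second reply is that the plan already compares demographics between groups, so a serious age gap would show. That is partly right. At 0.4/0.4 the gap of 0.64 SD would be significant about 83% of the time (0.638/0.220 = 2.91 standard errors). At 0.3/0.3 it would be missed about 41% of the time (0.479/0.220 = 2.18 standard errors). A balance test is also not an adjustment, and the plan does not say what would follow from a significant result.

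Third, interval is the weaker candidate. A 3-month gap would be 3/3.32 = 0.90 SD, which under a median split implies a correlation of 0.90/1.596 = 0.57 between interval and fitness change. That is unlikely, so the upper end of the interval bias should be read as a bound. Interval still belongs in the model, because it varies and the visit dates should be on file.

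Finally, the simulations cover the between-subjects contrast only and show nothing about Fitness × Congruency. Any added model also comes after data collection. Both are true; the second is why the registered analysis should stay in place.

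**Conclusion.** The concern holds. The plan compares self-formed groups on change while naming Gender as the only covariate, and nothing elsewhere in the document adds age or interval. The size of the problem cannot be known from the documents. Under the assumptions listed, omitting age is harmless when its correlations with fitness change and outcome change are about 0.2 or less. It roughly doubles the false-positive rate at 0.3/0.3 and raises it three- to fourfold at 0.4/0.4. The corresponding biases are 0.06, 0.14 to 0.15 and 0.26 SD of the change score. Interval adds 0.01 to 0.13 SD, with the upper end unlikely. The exposure is confined to the Fitness main effect; the ApoE4 × Fitness interaction is affected only if the confounding differs by genotype. This should be addressed, with medium confidence that it would alter the result.

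**What to change.** Keep the registered Gender-only ANOVA and state explicitly that Gender is in the difference-score models. Beside it, repeat each difference-score ANOVA with mean-centred baseline age and months between visits added, including their interactions with Congruency. Label these models as added after data collection: study conduct ended 5/1/2021 and the document is dated 2022/12/12. Tabulate age, months between visits and baseline outcomes for the four groups, and say whether 3.32 is a standard deviation or a window.

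Two further analyses are optional, as sensitivity checks only:

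- Adjust for baseline outcome, analysing the condition mean and the incongruent-minus-congruent score separately, each with its own baseline. In non-randomised groups this answers a different question from the change score.
- Add age × ApoE4 when testing the interaction hypothesis. With 20% carriers the smallest cell has a median of 7 people in the simulation, so this model should be read cautiously.

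The cost is a wording change, one extra set of results and one table. No new data should be needed: age is recorded, and the reported interval implies that visit dates are held.
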